The purpose of the present study is to determine if a multilevel intervention (consisting of community events at local walking trails, formation of walking groups, and text messaging) will increase physical activity among rural residents. Intervention community members will receive the multilevel intervention while control communities will not. In the intervention communities, it is preferable for all participants to partake in all aspects of the intervention; however, not every person will partake in every level. We will create a dose-response variable hypothesizing participants who take part in all aspects of the intervention (i.e., attend walking events, takes part in walking groups, and receives text messages) will increase their physical activity more than people who engage in less of the intervention and those in control communities. As a part of the walking group formation in intervention sites, we will be utilizing the Stanford Healthy Neighborhood Discovery Tool application in order to receive feedback from participants related to the walking trails in their towns.

1.4 Specify your research question(s), study aims or hypotheses:
Test the independent and moderating effects of a multilevel intervention and the community environment on physical activity among rural residents.

1.5 Background and significance and/or Preliminary studies related to this project:
Key informant interviews were conducted in the intervention communities with three groups of people, walking trail users, walking trail non users, and stakeholders. We received feedback on the best methods by which to utilize local walking trails in the communities. Further, participants indicated to us their willingness to partake in future aspects of the study. Walking trail users and walking trail non users may be asked to participate as participants, while stakeholders may be asked to partake in a coalition to partner in increasing physical activity in rural southeast Missouri.

1.6 Literature cited/references (if attaching a grant enter N/A):

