1.20 What have you done to minimize any risks?

- No foreseeable risks

1.21 What are the potential benefits related to this project for:

- the participant (if any)
- benefits to society (if any)

An increase in physical activity may lead to improved health. The benefit to society is the project, if successful, has the potential to be scaled-up to reach a larger number of people.

1.22 Provide a summary of the analysis methods you will use, including, if applicable, the data points or outcomes you will analyze.

The intervention is at the community, interpersonal, and intrapersonal levels, and the activity environment is classified at the individual level. The basic model for the individual level analysis is: $Y_{jk} = \alpha_j + \beta I_{jk} + \gamma X_{jk} + \eta Z_{jk} + \theta I_{jk} * E_{jk} + \epsilon_{jk}$; where Y_{jk} is the change in physical activity for subject k in j th community ($j = 1, 2, \dots, 12$), $I_{jk} = 1$ if intervention and 0 otherwise, X = a vector of community level covariates, Z = a vector of individual level covariates (including E_{jk} individual level of activity environment), and $I_{jk} * E_{jk}$ = intervention-by-environment interaction. The parameter α_j is the random intercept, β is the main effect for intervention, and θ is the interaction effect. In this model, β is the expected difference in the physical activity level between intervention and control among those whose physical activity is mainly indoor, and $(\theta + \beta)$ is the expected difference in the physical activity level between intervention and control among those whose physical activity is mainly in the natural environment. Both main and

interaction effects are adjusted for community level and individual level covariates. The primary analyses will be conducted at the end of 1 and 2 year follow-up. In these analyses, baseline physical activity level will be used as one of covariates.

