1.23 Provide the rationale or power analysis to support the number of participants proposed to complete this study. This study uses a paired, group-randomized design. By using matching criteria, we will balance potential community-level confounding factors (e.g., community size, poverty level) with a gain in the statistical power [9,10]. Based on the literature, we estimated accelerometer-measured MVPA in the control group at 42.5 minutes per week (m/w). [9] In the intervention group, we assume a 16% increase (42.5*1.16 = 49.3), based on a recent meta-analysis [11]. We used a much larger SD of 16 rather than that reported (6.2) to ensure a sufficient sample size both for testing the intervention effect and for testing the intervention-by-environment interaction (moderation) effect. We assumed ICC estimates in the range of 0.01-0.03, based on our pilot studies and values of ICCs in the literature [12-18]. With 12 communities and an average of 48 study subjects in each (a total of 576 subjects for accelerometry), the study has power >90% with 2-sided $\alpha = 5\%$ to detect the mean difference in MVPA between the control (42.5) and intervention (49.3) groups, using Donner's method [19]. For intervention-by-environment interaction, we assume in the natural environment, the intervention and control difference is 57 m/w versus 44 m/w, and in the indoor environment, the difference is 43 m/w versus 41 m/w. Estimates of interaction are based on our pilot work and existing studies [20]. With a common SD in each of four subgroups = 10, we have 84% power to detect a significant interaction using factorial analysis of variance methods (F-test) adjusting for clustering (ICC = 0.03). Our simulation using two-level mixed effect models also indicates the power to detect the assumed interaction effect >90%. Our sample size is determined for accelerometry subjects at the end of Year 2. With a yearly follow-up rate of 80%, which is achievable given our previous work, we need to enroll 576/0.64 = 900 at baseline for accelerometry. For telephone survey subjects, we need to enroll 900/0.75 = 1,200 at baseline.

1.25 Will any data from this project be stored for use in future research studies?
No

1.26 Does this project involve the collection or use of biological samples or genetic data?
No

1.27 Are you requesting institutional certification to contribute human data or samples to a repository or database for broad sharing (public or restricted access)?
No

2. Participants

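### Both the 1-year and 2-year analyses are called primary with no ranking or multiplicity rule, although the study is sized only for Year 2, and the interaction's status is left unstated

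*Combined protocol and SAP*

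**What the plan says.** On timing, section 1.22 says: "The primary analyses will be conducted at the end of 1 and 2 year follow-up". Section 1.23, by contrast, says: "Our sample size is determined for accelerometry subjects at the end of Year 2".

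On hypotheses, section 1.4 gives one aim: "Test the independent and moderating effects of a multilevel intervention and the community environment on physical activity among rural residents". Section 1.22 fits one model containing an intervention term (beta) and an intervention-by-environment term (theta). It defines beta as the intervention-control difference among people who are active mainly indoors. Section 1.23 chose its SD so that the sample would suffice "both for testing the intervention effect and for testing the intervention-by-environment interaction (moderation) effect".

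On error rates, section 1.23 attaches a two-sided 5% to the intervention effect, with power above 90%. For the interaction it gives 84% power for a significant result and states no significance level.

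No section ranks the two years or the two effects, splits alpha, or sets a testing order. Section 1.13 describes baseline and a single follow-up, whereas section 1.7 asks participants to accept surveys at three time points.

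**The concern.** With two primary time points, each open to a test at 5%, the stated 5% is no longer the chance of a false primary claim on the intervention effect. A positive Year 1 result followed by a null Year 2 result could be reported as a positive primary finding, although the sample size was set for Year 2.

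The interaction adds a second ambiguity. It shares the only aim and has its own power figure, but a reader cannot tell whether a significant interaction with a null overall effect would make the trial positive. Nor does the model's beta answer the question that was sized. The subgroup means assumed in 1.23 imply an indoor difference of 43 - 41 = 2 minutes per week, against the sized overall difference of 49.3 - 42.5 = 6.8.

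**Working it through.** **Inputs from 1.23.** 12 communities of 48, total 576 (288 per arm, assuming six communities per arm); difference 6.8; SD 16; ICC 0.01-0.03; two-sided 5%. Interaction: (57 - 44) - (43 - 41) = 11; SD 10; ICC 0.03; stated power 84%. The documents give no correlations between test statistics, so those below are assumptions.

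**Step 1: reproduce the plan's power.** Design effect DE = 1 + (48 - 1) x ICC; SE = 16 x sqrt(2 x DE / 288); power = Phi(6.8/SE - 1.96).
- ICC 0.03: DE = 2.41, SE = 2.07, 6.8/2.07 = 3.285, power 90.7%.
- ICC 0.02: 95.6%. ICC 0.01: 98.8%.

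The stated figure above 90% reproduces under the normal approximation, for one test at one time point using the whole 5%.

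**Step 2: can the interaction's significance level be recovered from its 84%?** With four equal cells of 144, SE = 10 x sqrt(4 x 2.41 / 144) = 2.587 and 11/2.587 = 4.25, so power at two-sided 5% is 98.9%, not 84%. An unstated 15/85 environment split gives 86%. The 84% therefore does not confirm a 5% level; using 5% for the interaction below is an assumption.

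**Step 3: one effect, two years.** The rate is 1 - P(|Z1| <= 1.96 and |Z2| <= 1.96) for bivariate normal statistics with correlation r, both nulls true. If independent, 1 - 0.95^2 = 9.75%. Simulation with 2 million draws gives:

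| r between years | 0.3 | 0.5 | 0.7 | 0.8 | 0.9 |
|---|---|---|---|---|---|
| False-claim rate | 9.5% | 9.1% | 8.3% | 7.8% | 7.0% |

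**Step 4: if the interaction also counts as primary at an assumed 5%.** The correlation between the two effects depends on which intervention parameter is tested. With an equal environment split, the overall difference is roughly uncorrelated with theta. The indoor beta has variance v, theta has variance 2v and their covariance is -v, so their correlation is -1/sqrt(2) = -0.71.

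| Family | Overall effect and theta (correlation 0) | Indoor beta and theta (-0.71) |
|---|---|---|
| Two effects, one time point | 9.75% | 8.3% |
| Four tests, r = 0.3 | 18.2% | 15.6% |
| Four tests, r = 0.5 | 17.3% | 14.8% |
| Four tests, r = 0.7 | 16.0% | 13.7% |
| Four tests, r = 0.9 | 13.6% | 11.5% |

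Four independent tests would give 1 - 0.95^4 = 18.5%.

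**Step 5: cost of the remedies, at ICC 0.03.** Bonferroni would cut power for the intervention effect from 90.7% to 85.2% over two tests (2.5% each) or 78.5% over four (1.25% each). Ranking leaves it at 90.7%. Testing the interaction only after a significant overall effect, with the two treated as independent, gives 0.91 x 0.84 = about 76% power to claim the interaction. With the 98.9% of Step 2 in place of 84%, it is 0.907 x 0.989 = about 90%.

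**The case against.** The strongest objection is that the documents do not define four primary tests. A reader might infer that both effects are sized at a full two-sided 5%, that a significant result on any of four tests counts as success, and that the false-positive rate is therefore somewhere between 8% and 18%. The text does not support that reading. The 5% is written for the intervention effect only. The interaction is never called primary, and no success rule is stated. A single 8-18% range would also merge a two-test family with a four-test family. This part of the objection stands, so the figures are kept apart and labelled by family.

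Second, section 1.13 has one follow-up. If that is correct, the Year 1/Year 2 multiplicity disappears along with every four-test figure, and what remains is the unranked interaction. This also stands, as a condition on the result. But 1.22 as written has two primary time points, and 1.7 expects three surveys.

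Third, whether the intervention works and whether environment moderates it are distinct questions, and joint error control over them in a behavioural trial is partly a matter of judgement. That is fair, and gating the interaction is a real trade-off because moderation is half of the aim. It does not excuse leaving the interaction's rank unstated, and it does not touch the time-point problem, which concerns one effect tested twice.

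Finally, 1.22 answers a request for a summary, and a grant package that was not available for this review is listed in section 2.1. That lowers certainty. However, section 1.1 says no separate protocol will be submitted.

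**Conclusion.** The concern holds for the time points. Followed as written, with each year tested at 5%, the chance of a false primary claim on the intervention effect is about 7% to 9.5%, for assumed between-year correlations of 0.9 to 0.3 and provided both follow-ups are collected.

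For the interaction, the supportable conclusion is that its status is undefined. Only if it is treated as primary at an assumed 5% does the rate become about 8-10% (two effects at one time point) or about 11-18% (four tests, both follow-ups collected). With a single follow-up and a secondary interaction, the 5% would stand.

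The gap should be closed before analysis. It affects which result can be called the trial's finding, and does not call the Year 2 sample-size calculation into question.

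**What to change.** In section 1.22:

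1. Name the Year 2 analysis, which 1.23 already sizes, as the single primary time point, and label Year 1 secondary.
2. State that the primary hypothesis is the overall intervention-control difference sized in 1.23, tested at two-sided 5%. Say how it is estimated: from the model without the interaction term, or as a defined marginal contrast. Naming beta from the present model would not do this.
3. State the interaction's rank: either secondary, or tested at 5% only after the overall effect is significant.
4. Reconcile 1.13 with 1.22 on the number of follow-ups. If only one is collected, apply the same ranking of the two effects to it.

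The cost is a few sentences. No participants are added, and the Year 2 overall test keeps its power. Year 1 loses primary status. If the interaction is gated, the power to claim it falls somewhat, for example to about 76% on the plan's own 84%; if it is made secondary, it can no longer carry a primary claim.

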To recruit intervention community participants Washington University in St. Louis (WashU) project staff will reach out via telephone to those walking trail users and walking trail non users to determine their current interest in participating in this study (see section 1.5) using the telephone script. Further, WashU project staff will reach out to stakeholders to determine their interest in being a part of a coalition - in this capacity, project staff will use the informational sheet to reach out to stakeholder constituents to determine their interest in partaking in the study.

Recruitment in control communities is detailed elsewhere. Participants in both intervention and control communities may provide their consent immediately after asking any questions, or project staff can call the potential participant back at a later time (typically within a week). It will be stated to participants that participation is completely voluntary, and they are welcome to withdraw at any time.

1.13 Provide a detailed description in sequential order of the study procedures following the consent process - DO NOT cut and paste from the Consent Document.

Describe study populations separately if they will be participating in different procedures

DESCRIBE:

- Control populations, if applicable
- Any randomization, if applicable
- What participants will be asked to do/what happens in the study (in sequential order)
- The time period over which procedures will occur
- Long-term follow-up and how it occurs

Control and intervention participants will conduct a telephone survey at baseline and one follow-up timepoint (n=1241). A subset recruited from the baseline telephone survey, will wear an accelerometer and global positioning devices for one

week at baseline and one follow-up timepoint(n=300).

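### The 84% power for the intervention-by-environment interaction does not follow from its stated inputs, which give about 99%, and the change from SD 16 to SD 10 is not explained

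*Combined protocol and SAP*

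**What the plan says.** All the power figures are in section 1.23. The main-effect calculation compares 42.5 with 49.3 minutes of MVPA per week, with 12 communities averaging 48 subjects (576 in all) and two-sided alpha 5%, and claims power above 90%. On the SD it says: "We used a much larger SD of 16 rather than that reported (6.2) to ensure a sufficient sample size both for testing". That sentence names two targets. The first is the main effect; the second is given in these words: "and for testing the intervention-by-environment interaction (moderation) effect". On clustering it says: "We assumed ICC estimates in the range of 0.01-0.03".

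For the interaction, it assumes that in the natural environment "the intervention and control difference is 57 m/w versus 44 m/w", and that indoors the means are 43 and 41. It then states: "With a common SD in each of four subgroups = 10, we have 84% power to detect a significant interaction". The test is a factorial F-test adjusted for clustering with ICC 0.03. A second figure for the same effect follows: "Our simulation using two-level mixed effect models also indicates the power to detect the assumed interaction effect >90" percent. The share of subjects in each environment is not stated.

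Section 1.22 adds that "the activity environment is classified at the individual level" and specifies a model with a random community intercept and an intervention-by-environment term.

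**The concern.** The contrast of 11 minutes per week is larger than the SD of 10. With 576 subjects, even after a design effect of 2.41, power should be well above 84%. The SD also falls from 16 to 10 a few sentences after 16 was said to have been chosen with both tests in view.

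Moderation by the environment is part of the only aim in section 1.4. It rests on two power figures: one that its own inputs do not give, and one whose SD and ICC are not stated. A reader cannot tell which assumptions support the interaction claim, and by the plan's F-test approach the choice of SD moves the answer by more than 20 percentage points.

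**Working it through.** **Inputs, all from section 1.23 unless marked.** Means 57 and 44 (natural), 43 and 41 (indoor); SD 10; ICC 0.03; 12 communities of 48, so 576. This number is already the Year 2 count, so no dropout reduction applies. Two-sided alpha 5% is stated for the main effect and assumed here for the interaction. An even environment split is also assumed.

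**Step 1: reproduce the plan's main-effect figure.**
- Design effect = 1 + (48 − 1) × 0.03 = 2.41.
- z = 6.8 / √(16² × 2.41 × 4 / 576) = 3.285.
- Power = Φ(3.285 − 1.960) = 90.7%.

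This agrees with the stated figure of above 90%, so the design effect is in line with the plan's method.

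**Step 2: interaction power as stated.**
- Contrast = (57 − 44) − (43 − 41) = 11.
- Effective N = 576 / 2.41 = 239.
- For four equal cells, f = 11 / (4 × SD) = 2.75 / 10 = 0.275.
- Noncentrality λ = 239 × 0.275² = 18.07.
- F-test with 1 and 235 df: power **98.9%**, against 84% printed.

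**Step 3: look for a reading that gives 84% at SD 10.**

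| Change from step 2 | Power |
|---|---|
| ICC 0.02 | 99.7% |
| ICC 0.01 | above 99.9% |
| 10 denominator df | 96.8% |
| 8 denominator df | 95.9% |
| 5 denominator df (six pairs) | 92.0% |
| Split 45:55 | 98.8% |
| Split 30:70 | 97.3% |
| Split 20:80 | 92.3% |

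Changing one input at a time, 84% needs one of the following:
- an ICC of 0.083, outside the plan's 0.01 to 0.03;
- about 283 subjects instead of 576;
- an SD of 14.3 instead of 10;
- an 86:14 split in either direction.

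The first three contradict stated values. The split is unstated, but it can be checked against the arm means:
- Even split: intervention (57 + 43)/2 = 50.0; control (44 + 41)/2 = 42.5.
- 45% natural: intervention 49.3; control 42.35.
- 86% natural: 55.0 and 43.6.
- 14% natural: 45.0 and 41.4.

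The plan uses 49.3 and 42.5, so a roughly even split fits and 86:14 does not.

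**Step 4: SD 16 in the same calculation.** f = 2.75 / 16 = 0.172 and λ = 7.06, giving **75.4%** at ICC 0.03. At ICC 0.02 the power is 83.9%. That match with 84% may point to mislabelled inputs, but the documents do not say so.

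**Step 5: can SD 10 be the within-subgroup version of an arm SD of 16?** With an even split, each arm's variance is the subgroup variance plus the squared half-difference between its subgroup means (7 for intervention, 1.5 for control).
- From SD 10: √(100 + 49) = 12.2 and √(100 + 2.25) = 10.1, not 16.
- Working back from an arm SD of 16: √(256 − 49) = 14.4 and √(256 − 2.25) = 15.9, pooled 15.2.

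**Step 6: the model in section 1.22.** If environment varies within communities and only the intercept is random, the community effect cancels from the interaction contrast and the variance factor is 1 − ICC = 0.97 instead of 2.41. At SD 16, ICC 0.03 and 576 subjects, power is 98.7% (98.8% in 8,000 simulated trials).

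**The case against.** The strongest reply is that 99% is not uniquely determined. The plan gives neither the split nor the denominator df for this test, and it describes a paired design. With 5 pair df, power is 92.0%. Joint changes need less extreme values than the single changes above: a 25:75 split with 5 df gives 83.4%, and a 20:80 split with 8 df gives 84.5%. The arm means and subgroup means also come from different sources, so matching them is an inference. This stands in part: 98.9% is conditional on a roughly even split and residual df. But the joint readings need community-level df, which the stated factorial F-test does not suggest, and they imply arm means of about 46.5 and 41.8, or 45.8 and 41.6, against 49.3 and 42.5.

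The SD sentence can also be read differently: SD 16 may have been used only to inflate the main-effect sample so that it would also cover the interaction. On that reading the two SDs do not conflict. The 84% still does not follow from SD 10.

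Finally, the consequence is limited. At SD 10 the printed value understates power, the simulation figure points the same way, and the sample size follows from the main-effect calculation (576 / 0.64 = 900). The 75% at SD 16 applies the full design effect, which is conservative for the model in section 1.22. All of this stands, and it limits the point to a power statement that cannot be reproduced.

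**Conclusion.** The concern holds. On the stated inputs the interaction power is about 99%, some 15 points above the printed 84%. It stays at 92% or more with the fewest plausible denominator df and an even split. This rests on a roughly even environment split, which the plan does not state but its arm means support.

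The use of SD 10 after SD 16 is unexplained, and forming subgroups does not account for it. The simulated figure of above 90% is not shown to be wrong, but it cannot be checked without its SD and ICC. The finding does not show that the planned random-intercept analysis is underpowered at 576 subjects.

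**What to change.** In section 1.23:
- State one SD for the interaction. Either use a value consistent with the main-effect calculation (within-subgroup about 15.2 to 16 for an arm SD of 16) or justify 10.
- State the ICC, the environment split, the denominator df and a clustering adjustment that matches the section 1.22 model.
- Recompute and replace the 84%.
- Give the SD and ICC behind the simulation.

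Two separate inconsistencies should be settled at the same time, because the recalculation needs the answers. Section 1.13 describes the accelerometry subset as measured for one "week at baseline and one follow-up timepoint(n=300"), whereas section 1.23 has 900 enrolled and 576 remaining at Year 2. Section 1.7 has 14 communities (seven per arm), whereas sections 1.22 and 1.23 have 12.

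Only if 300 is the real baseline number does the interaction power need restating for it. At SD 15.2 to 16, ICC 0.03, 14 communities and the random-intercept model, it would be about 77% to 81% with 300 × 0.80 = 240 completers, and 67% to 72% with 300 × 0.64 = 192.

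The cost is recalculation and rewording. The restated power may be higher or lower than 84%, depending on the SD and sample adopted.
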